	
for several weeks; 6.4 mg daily, 4 days a week, for 2 weeks out of every month up to 6 months in duration; and 16 mg twice a week for four weeks, with few adverse events observed. The proposal to evaluate Ta1 at a dose of 1.6 mg is based on previous studies which have shown an increase in dose above 1.6 mg to show little, if any, improvement in response.
 
Patients with end-stage renal disease (ESRD) on hemodialysis, in addition to their intrinsic kidney disease and frequent burden of comorbidities, also have increased risk of exposure to communicable diseases as they are treated several times each week at hemodialysis centers with several other patients and clinic staff in attendance. The majority of patients are over 60 years of age and many are receiving immunosuppressive medications. Accordingly, ESRD patients are particularly susceptible to COVID-19 infection. Ta1 has been shown to be safely administered to hemodialysis patients on a similar schedule to that proposed below, and was efficacious in enhancing influenza vaccine responses [1].

Objectives:	
Primary Objective
 
To demonstrate that Ta1 administered twice weekly for eight weeks to renal dialysis patients 60 years and older will reduce the incidence of COVID-19 infection compared with a similar population of patients who do not receive Ta1.
 
Secondary Objectives
 
1. To demonstrate that renal dialysis patients treated with Ta1 who become infected with COVID-19 will have a milder course of infection in terms of hospitalization rate, requirement (length) for ICU stay, requirement for mechanical ventilation, and survival than renal dialysis patients not treated with Ta1.2. To demonstrate a decrease in hospitalization rates in renal dialysis patients treated with Ta1 who are not infected with COVID-19 compared to those not treated with Ta1.
Study Design:	
It is our hypothesis that a course of Ta1 administered to individuals at high risk for COVID-19 infection will reduce the rate of infection (primary objective) and severity of infection (secondary objective) with COVID-19, compared to untreated individuals in the same hemodialysis units with

Clinical Study Protocol: Ta1 to Prevent COVID-19 Infection in Elderly Renal Dialysis Patients

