6 OBJECTIVES

6.1 Primary Objective

Primary Objective

To demonstrate that Ta1 administered twice weekly after dialysis for eight weeks to renal dialysis patients 60 years and older will reduce the incidence of COVID-19 infection over a six-month period compared with a similar population of patients who do not receive Ta1.

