6.2 Secondary Objectives

Secondary Objectives:

1. To demonstrate that renal dialysis patients 60 years and older treated with Ta1 who become infected with COVID-19 will have a milder course of infection in terms of hospitalization rate, requirement for and length of ICU stay, requirement for mechanical ventilation, and survival than renal dialysis patients not treated with Ta1.
2. To demonstrate a decrease in hospitalization rates in renal dialysis patients treated with Ta1 who are not infected with COVID-19 compared to those not treated with Ta1.

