8 ENDPOINTS

8.1 Primary Endpoint

The primary efficacy endpoint is reduction in documented infection with COVID-19. This is defined as clinical suspicion (presence of symptoms of respiratory infection; see Appendix 1 for questionnaire) and laboratory confirmation of COVID-19 infection.

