Each sample size calculation depends on the type of endpoints, the variability of data, analysis methods used, and the minimal difference (or effect size) that we wish to be able to detect between the treatment (with Zadaxin) or control (without Zadaxin) groups. There are four types of endpoints for this study, dichotomous (e.g., infection of COVID19, the primary endpoint; ICU admission; or mortality), polytomous (e.g., health changes: no change, moderate, severe changes), counts (e.g., occurrence of non-COVID-19 infections), or continuous outcome variables (e.g., CD4, CD8, CD4/CD8, length of hospital stay, recovery time from COVID19). For a dichotomous outcome, a suitable model is a logistic regression with the treatment status (treated or not treated with Zadaxin) as the primary covariate, demographic information (age, gender, race), health/medical information (e.g., Karnofsky score, co-morbidity, and other biomarkers) and environmental information (treatment center, among others) as other relevant covariates. Assume the infection rate for the control group is about 0.40 and with a significance level of 0.05 (unless specified otherwise), if we use a simple logistic regression, a sample of size 200 will be able to detect a change at least at 0.185 in the infection rates between the treatment and control groups with a power of 80%. If we have a bigger sample size, say 234, we would be able to detect a change with a minimal difference of 0.17 with the same power or a minimum difference of 0.185 with a power of 86.5%. Using more comprehensive procedures (below) or if the actual difference is (much) larger than the minimal difference, we will have a (much) higher power than 80% to detect the actual difference. If we make a conservative adjustment for multiple comparisons incorporating other covariates after a pre-screening step, at an adjusted significance level 0.005, a sample of size 205 will provide 80% power for detecting a change of at least as large as 0.23. Using a multiple logistic regression model that takes into account the correlation among the various covariates, say if the correlation is 0.2, we can detect a minimal difference at 0.202 with a sample size of 200. If the correlation is 0.5, the minimum detectable difference would be 0.25. The highly correlated covariates that lead to multicollinearity will indicate the need for removal of redundant covariates in modeling the endpoint, and the removal will lead to more degrees of freedom in our study and the same power in detecting the even smaller difference. We will use all the sample we have and incorporate censored data or treat missing information with survival or a more comprehensive model than the logistic regression; thus, we expect to be able to detect a smaller minimal difference or have a much higher power to detect the actual difference in the infection rates than given above.

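### Secondary objective 1 judges COVID-19 severity among patients infected after randomisation, so randomisation does not protect the comparison, which could mislead in either direction and has low power

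*Combined protocol and SAP*

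**What the plan says.** Section 6.2, item 1, concerns patients "treated with Ta1 who become infected with COVID-19 will have a milder course of infection in terms of hospitalization rate", and adds ICU stay, ventilation and survival. The synopsis has the same objective: "renal dialysis patients treated with Ta1 who become infected with COVID-19 will have a milder course of infection". Both are worded as something to be demonstrated. The comparator in 6.2 is given only as "requirement for mechanical ventilation, and survival than renal dialysis patients not treated with Ta1". It is not expressly limited to infected controls, but an uninfected patient has no course of infection, so infected controls are implied.

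Section 6.1 states the primary hypothesis that Ta1 "will reduce the incidence of COVID-19 infection over a six-month period". Section 8.1 defines a documented infection by laboratory confirmation together with clinical suspicion ("presence of symptoms of respiratory infection; see Appendix 1 for questionnaire").

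Section 8.2 lists hospitalisation, ICU admission, ventilation and mortality, mostly without limiting them to infected patients, and section 11.1 collects them for all subjects. Section 15.1 places age, Karnofsky score and comorbidity among the covariates of the logistic model. Section 15.2 assigns a regression type to each kind of outcome. It names no analysis population for severity and no COVID-19-specific severity analysis in all randomised patients.

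**The concern.** Randomisation makes the two arms comparable at entry. It does not do so for the subsets later infected if treatment influences who enters them, which is what the primary objective hopes for. If Ta1 prevents infection mainly in sturdier patients, the remaining Ta1 cases are frailer than the control cases and look sicker, even if the drug leaves the course of disease unchanged. If it mainly protects the frail, the reverse happens.

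The conclusion about a milder course is what is at stake: its sign could reflect which infections were prevented rather than how severe they were. The comparison also rests on a minority of the trial's patients, and no sample-size statement covers that subset.

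**Working it through.** **1. Reproduce the plan's own figure.** Inputs from section 15.1: "Assume the infection rate for the control group is about 0.40 and with a significance level of 0.05", and "a sample of size 200 will be able to detect a change at least at 0.185 in the infection rates" at 80% power. Allocation is 1:1 (section 10.5), so 100 per arm. The Ta1 rate is 0.40 − 0.185 = 0.215.

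Power = Φ[(|p1 − p2| − 1.96·s0)/s1], where s0 = √[p̄(1 − p̄)(1/n1 + 1/n2)] and s1 = √[p1(1 − p1)/n1 + p2(1 − p2)/n2].

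Here p̄ = 0.3075, s0 = 0.0653, s1 = 0.0639. Power = Φ[(0.185 − 0.1279)/0.0639] = 81%, against the stated 80%. The plan's figure reproduces with a two-sided test.

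**2. Size of the infected group.** Controls: 100 × 0.40 = 40. Ta1: 100 × 0.215 = 21.5, about 22. Total about 62 of 200.

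**3. Distortion with no drug effect on course.** The documents give no risk split and no hospitalisation rate among the infected. Assumed: half the patients frail and half robust; hospitalisation given infection 50% and 10%; control infection 40% in both groups; overall Ta1 infection 21.5%. Infected controls then have (50% + 10%)/2 = 30% hospitalised. For Ta1 infection rates f (frail) and r (robust), the infected-only rate is (0.5f + 0.1r)/(f + r), and the all-randomised COVID-19 hospitalisation rate is (0.5f + 0.1r)/2. The control all-randomised rate is 0.40 × 0.30 = 12%.

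| Ta1 infection, frail / robust | Infected-only, Ta1 vs control | Distortion | All randomised, Ta1 vs control |
|---|---|---|---|
| 21.5% / 21.5% | 30.0% vs 30% | 0 | 6.5% vs 12% |
| 25% / 18% | 33.3% vs 30% | +3.3 points | 7.2% vs 12% |
| 18% / 25% | 26.7% vs 30% | −3.3 points | 5.8% vs 12% |
| 33% / 10% | 40.7% vs 30% | +10.7 points | 8.8% vs 12% |
| 10% / 33% | 19.3% vs 30% | −10.7 points | 4.2% vs 12% |

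The last two rows need strong effect modification: infection risk ratios of 0.33/0.40 = 0.825 in one half and 0.10/0.40 = 0.25 in the other.

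**4. Power of the infected-only comparison** (40 vs 21.5, formula above), for a true halving of hospitalisation:
- 30% to 15%: s0 = 0.1154, s1 = 0.1057, power 24%.
- 50% to 25%: s0 = 0.1316, s1 = 0.1224, power 47%.

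For a halving of ventilation or death from an assumed 10% or 20% (40 vs 22), power is 8% or 15%.

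**5. What the all-randomised analysis does and does not gain** (100 per arm):
- Ta1 reduces infection and halves hospitalisation given infection: 12% vs 0.215 × 15% = 3.2%, power 65%.
- Ta1 halves hospitalisation given infection but leaves infection at 40%: 12% vs 6%, power 32%. Infected-only (40 vs 40, 30% vs 15%) has 36%.
- Ta1 reduces infection but not the course: 12% vs 0.215 × 30% = 6.45%, and the test still rejects 27% of the time.

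The all-randomised comparison is therefore a valid test of whether Ta1 reduces severe COVID-19, but it does not isolate severity given infection.

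**The case against.** Several points on the other side stand.

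- **Adjustment is planned.** In the example above frailty is the only source of distortion. A model that fully captured it would remove the false signal, because hospitalisation within each risk group is the same in both arms. Karnofsky score and comorbidity go some way towards this. Risk factors that are unmeasured or poorly measured remain.
- **The endpoints are not confined to infected patients.** A reader might infer that the plan has no all-randomised version of these outcomes. That is too strong: section 8.2 mostly does not restrict them, and section 15.1 treats ICU admission and mortality as outcomes compared between arms. What is missing is a COVID-19-specific version tied to objective 1.
- **Symptomless infection would not go unseen.** A reader might infer from section 8.1 that cases made symptomless by Ta1 vanish from the data. Table 1 schedules a SARS-CoV2 assay for everyone at weeks 2, 4, 6 and 8 and months 3 to 6, and section 11.1 stores serum for antibody testing. Such cases can be found. What remains is that objective 1 does not say whether they count as infected.
- **The power contrast is not like for like.** A reader might set 24% beside 65% and conclude that the all-randomised analysis is better powered for severity. The 65% includes the assumed drop in infection. Without that drop the figures are 36% infected-only and 32% all-randomised.

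It is also fair that this is a secondary objective in a self-described pilot, and that the primary comparison is unaffected.

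**Conclusion.** The point holds as a limit on what objective 1 can show. It compares groups formed after randomisation by an event that Ta1 is intended to change, and the plan names no COVID-19 severity comparison that randomisation protects. Distortion arises only if Ta1 changes infection or diagnosis differently by underlying risk.

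The range of 0 to 11 points rests on assumed frailty and hospitalisation rates. A reader might take 11 points as the expected bias, or infer that the result will favour one arm. The documents support neither, since they give no effect modification and no severity rates. Power for hospitalisation is low (24% to 47% for a halving, at assumed control rates of 30% to 50%), and very low for ventilation and death at the assumed 10% to 20%.

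This is a worthwhile, low-cost change, not a condition for the trial's validity.

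**What to change.** In section 6.2, the synopsis and section 15.2:

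1. Make the inferential comparison for objective 1 COVID-19 hospitalisation, COVID-19 ICU admission, COVID-19 mechanical ventilation and all-cause death in all randomised patients over six months, with COVID-19-related death also reported. Count never-infected patients as having no COVID-19 event.
2. Keep ICU length of stay, counting COVID-19 ICU days as zero for patients without such a stay.
3. Report the infected-only comparison, adjusted for baseline risk, as descriptive and not protected by randomisation. State that the comparator is infected controls, and whether symptomless laboratory-confirmed cases are included.
4. State how the 40 anticipated dropouts enter the all-randomised analysis.

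The cost is wording. Subjects stay on study after a positive test (section 10.1) and the outcomes are already collected for everyone. A rule for attributing an admission to COVID-19 is needed, because section 8.2 makes that split only for mortality. The scientific cost is that the all-randomised result combines fewer infections with milder ones. It should be reported as an effect on severe COVID-19, not as evidence of a milder course.

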	
comparable risk. The secondary objectives also include an evaluation of the need for hospitalization in those patients who do not become infected with COVID-19.
 
Ideally, a randomized clinical trial with placebo control would be a preferred approach to address this hypothesis. However, the urgency of the current situation necessitates a simpler research design and implementation. Accordingly, we consider this a pilot study from which meaningful clinical data may rapidly be apparent.
 
After screening, renal dialysis patients 60 years and older who meet the inclusion criteria will receive Ta1 (1.6 mg) administered subcutaneously (SC) twice weekly for eight weeks. Individuals in the control arm will be followed on the identical protocol but will not receive twice weekly Ta1. After the treatment period, all subjects will be followed for efficacy outcomes for an additional 4 months.

Sample Size:	A total of up to 240 patients will be enrolled
Countries:	U.S.
Study Period:	Once FDA and IRB approval are obtained, the research team will promptly initiate the process of subject recruitment. Recruitment of all subjects will be completed in four months and the observation phase in one year.
Diagnosis and Main Criteria for Inclusion:	
 1. Age 60 or greater 2. Signed informed consent 3. End-stage renal disease (ESRD) who receive hemodialysis 2 or more times each week and are expected to continue on dialysis indefinitely.
Main Exclusion Criteria:	
 1. Patients on short-term hemodialysis, such as those with transient renal dysfunction associated with acute illness who are projected to have return in renal function 2. Patients for whom renal transplantation is anticipated within the next six months 3. Patients with an anticipated survival of less than 3 months 4. Patients with symptoms that might be attributable to COVID-19 infection (see Appendix 1 for symptom questionnaire) 5. Patients who test positive for SARS-CoV2

Clinical Study Protocol: Ta1 to Prevent COVID-19 Infection in Elderly Renal Dialysis Patients

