7 STUDY DESIGN

[figure not shown]
It is our hypothesis that a course of Ta1 administered to individuals at high risk for COVID-19 infection (hemodialysis patients 60 years and older) will reduce the rate of COVID-19 infection (primary objective) and severity of infection (secondary objective) with COVID-19, compared to untreated individuals in the same hemodialysis units with comparable risk. The secondary objectives also include an evaluation of the need for hospitalization in those patients who do not become infected with COVID-19.

Ideally, a randomized clinical trial with placebo control would be a preferred approach to address this hypothesis. However, the urgency of the current situation necessitates a simpler research design and implementation. Accordingly, we consider this a pilot study from which meaningful clinical data may rapidly be apparent.

After screening, renal dialysis patients 60 years and older who meet the inclusion criteria will receive Ta1 (1.6 mg) administered SC twice weekly for eight weeks. Individuals in the control arm will be followed on the identical protocol but will not receive twice weekly Ta1. After the treatment period, all subjects will be followed for efficacy outcomes for an additional 4 months. The total duration of the trial will be 1 year, including the estimated time required for screening.

A schema outlining the study design is presented in [Figure 1](#).

Figure 1: Study Design Schema

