8.2 Secondary Efficacy Endpoints

The secondary efficacy endpoints are:

1. Need for hospitalization
 - This is defined by documentation in the case report form (CRF) of physician referral to hospital for admission
2. Hospital length of stay
 - The number of overnight stays in the hospital, entered into the CRF
3. ICU admission
 - Documentation in the CRF of physician recommendation for ICU transfer.
4. ICU length of stay
 - The number of overnight stays in the ICU
5. Mechanical ventilation
 - Documentation in the CRF of administration of mechanical respiratory assistance and length of time such assistance required
6. Duration of mechanical ventilation
 - Documented in the CRF by physician
7. Recovery time from COVID-19
 - Defined as testing negative, plus the time for full recovery as determined by physician
 - Documented in the CRF by physician
8. Change in any existing comorbidities (e.g., worsening congestive heart failure) or newly diagnosed disease
 - Documented in the CRF by physician
9. Incidence of secondary non-COVID-19 infections (relapses, superinfections and new infections).
 - Documented in the CRF by physician
10. Change in T lymphocyte subsets (CD4, CD8)
 - Samples taken at enrollment, at 8 weeks and at 6 months, or at time of hospital admission if that is required
11. Mortality
 - COVID-19 related, or non-COVID-19 related; documented in the CRF by physician.

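### Secondary objective 2 does not fix the infection status of its comparator: one reading makes an inert drug look beneficial, and the other still selects on a post-randomisation outcome

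*Combined protocol and SAP*

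**What the plan says.** Section 6.2, item 2, with the same wording in the synopsis, aims to show that hospitalization is less frequent in "renal dialysis patients treated with Ta1 who are not infected with COVID-19 compared to those not treated with Ta1". The comparator is given only as patients not treated with Ta1, and the sentence does not say whether they too must be uninfected.

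Section 7 restates the objective as "an evaluation of the need for hospitalization in those patients who do not become infected with COVID-19", and the synopsis design text does the same. Neither singles out an arm.

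For the hospitalization endpoint, Section 8.2, item 1 says: "This is defined by documentation in the case report form (CRF) of physician referral to hospital for admission". It does not separate COVID-19 from other admissions. Section 15.2 assigns logistic regression to binary outcomes but names no analysis population for this comparison.

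The documents give no hospitalization rates. The only related planning figure is in Section 15.1: "Assume the infection rate for the control group is about 0.40 and with a significance level of 0.05".

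**The concern.** Two comparisons fit the text, and each has a problem.

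- **Uninfected Ta1 patients versus all controls.** The endpoint counts any referral for admission. Admissions caused by COVID-19 would be removed from the Ta1 side and kept on the control side, so a drug with no effect would be expected to show fewer hospitalizations.
- **Uninfected versus uninfected.** This treats the arms alike, but the groups are formed by infection status during follow-up, and infection is the outcome Ta1 is meant to reduce. If Ta1 works, more controls than Ta1 patients are removed and the remaining groups are no longer protected by randomisation. A patient admitted for another reason and infected later also leaves the comparison, and that admission goes too.

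The objective is worded as a demonstration of benefit. If the choice between readings is left until data are in hand, the apparent result could depend on it.

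**Working it through.** **Inputs from the documents.** Control infection 0.40 and significance level 0.05 (Section 15.1; two-sided assumed, since sidedness is not stated); 1:1 allocation (Section 10.5); about 200 patients with complete data (Section 15.1), so 100 per arm; minimum detectable difference 0.185 (Section 15.1).

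**Assumed inputs.** Six-month non-COVID-19 admission risk *b* of 20% to 40%; probability *c* of 20% to 60% that an infected patient is admitted for COVID-19; infection independent of *b* except in step 4. Infection of 10% is added as a low case, because Section 15.1 itself presents 40% as speculative.

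**1. The plan's own figure.** A pooled two-proportion test of 0.40 versus 0.40 − 0.185 = 0.215 needs 97 per arm (194 in total) for 80% power; at 200 the power is 81.4%. A difference of 0.17 needs 117 per arm, which is the plan's 234. The planning basis is reproduced closely.

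**2. Literal reading, inert drug.** With infection rate *p* in both arms:

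- uninfected Ta1 patients: *b*
- all controls: *b* + (1 − *b*) × *p* × *c*
- false benefit: (1 − *b*) × *p* × *c*

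Example with *p* = 0.40, *b* = 0.20, *c* = 0.20: 0.20 + 0.80 × 0.40 × 0.20 = 0.264, a gap of 6.4 points. Group sizes are 100 controls and 100 × (1 − *p*) Ta1 patients, i.e. 60 or 90.

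| *p* | *b* | *c* | Controls | Uninfected Ta1 | False benefit (points) | Significant for Ta1 |
|---|---|---|---|---|---|---|
| 0.40 | 0.40 | 0.20 | 44.8% | 40% | 4.8 | 8.5% |
| 0.40 | 0.40 | 0.60 | 54.4% | 40% | 14.4 | 42% |
| 0.40 | 0.20 | 0.20 | 26.4% | 20% | 6.4 | 14% |
| 0.40 | 0.20 | 0.60 | 39.2% | 20% | 19.2 | 73% |
| 0.10 | 0.40 | 0.20 | 41.2% | 40% | 1.2 | 3.7% |
| 0.10 | 0.20 | 0.60 | 24.8% | 20% | 4.8 | 12% |

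The nominal rate in that direction is 2.5%.

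**3. Symmetric reading, inert drug.** Both groups have risk *b*, so the expected difference is 0. Simulation gives a significant result favouring Ta1 in about 2.5% of trials.

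**4. Symmetric reading, effective drug.** Suppose infection is 40% in controls and 21.5% on Ta1. The uninfected number 60 + 78.5 = 138.5, about 139 of 200. If infection risk is unrelated to other admission risk, the bias is 0.

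Now suppose half the patients are frail, with infection risk 55% versus 25% in the non-frail (average 40%) and other-admission risk 60% versus 20%. Ta1 multiplies infection risk by 0.215 / 0.40 = 0.5375, giving 29.6% and 13.4%, and does not affect other admissions.

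- Uninfected controls: (0.5 × 0.45 × 0.60 + 0.5 × 0.75 × 0.20) / 0.60 = 0.210 / 0.60 = 35.0%
- Uninfected Ta1: (0.352 × 0.60 + 0.433 × 0.20) / 0.785 = 0.298 / 0.785 = 37.9%

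That is about 3 points against Ta1. A milder mix (other-admission risk 35% versus 15%, infection halved) gives 22.5% versus 24.1%, or 1.6 points.

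**The case against.** A reader might infer that the plan has committed itself to comparing uninfected Ta1 patients with every control. The documents do not support that. Section 7 and the synopsis describe hospitalization in patients who stay uninfected, without naming an arm. Objective 1 also puts its qualifier (becoming infected) on the Ta1 side only; taken literally it would compare the course of infection with that of controls who were never infected, which makes no sense. The drafter probably left out the repeated qualifier in both objectives, so uninfected versus uninfected is the more natural reading. The large false-benefit figures therefore belong to the less likely reading only.

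It can also be said that every admission rate here is assumed, that 40% infection is speculative, that 21.5% is only the control rate less a minimum detectable difference, that the frailty mix is illustrative, and that this is a self-described pilot. Non-COVID-19 hospitalization in everyone is moreover a different quantity from the one the objective names.

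All of this limits the size of the problem. What remains is that the objective's sentence does not state the comparator's infection status, no analysis population resolves it, and even the natural reading selects on an outcome the drug is meant to change.

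**Conclusion.** The concern holds as a matter of ambiguous wording and a missing analysis population, not as a confirmed asymmetric comparison.

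- On the literal reading, an inert drug tends to look beneficial: about 5 to 19 points at 40% infection and 1 to 5 points at 10%, within the assumed admission risks.
- On the more natural reading that artefact disappears. The remaining bias is small, 0 to 3 points against an effective drug, and its upper end depends on the assumed frailty mix. It would be too strong to say that an effective drug is necessarily penalised.
- On neither reading is the comparison, if Ta1 works, one of the groups as randomised.

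The plan should be corrected before data are reviewed. The point concerns a secondary objective and does not affect the primary comparison.

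**What to change.** Reword objective 2 as hospitalization from randomisation to month 6, compared by randomised arm in all randomised patients. Report all-cause admissions and, separately, admissions classed as COVID-19 or non-COVID-19. Use one classification rule, fixed before data are reviewed and applied identically in both arms, based on the assay results and hospitalization records the trial collects. Non-COVID-19 admissions of patients infected at another time then stay in the comparison. If an uninfected-only comparison is kept, apply the same restriction to both arms and label it descriptive.

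The cost is one reworded objective, one derivation rule and a check of the CRF. Sections 8.2 and 11.1 mention referral, overnight stays and hospitalizations but do not list admission dates, so it should be confirmed that these are captured.

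The downsides should be stated in the plan. Some admissions close to an infection will be misclassified. Later admissions for COVID-19 sequelae may count as non-COVID-19. COVID-19 deaths and stays reduce the time at risk for other admissions, unequally by arm if Ta1 works. The all-cause result does not depend on the classification, which is why the two should be read together.
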